4.4 Sample size calculation

The primary aim of this study is to provide estimates of the effect sizes of the primary and secondary outcome measures, and to estimate the inclusion rate so that we have sufficient input to determine feasibility of a future RCT and to yield input for the sample size calculation. Further design aspects, such as the need for multilevel analysis based on clusters of patients within hospitals will be assessed as well. A rule-of-thumb suggests including 12 patients per group in case of a pilot study, so that preliminary data on effect sizes and feasibility can be obtained. (30) For our study, this means 12 patients in the conventional RF group and 12 in the cooled RF group, but separately for patients with osteoarthritis and for patients with knee pain after total knee arthroplasty. Hence, we will include a total of 48 patients.

Cocogen Trial

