- The change in health-related quality of life, measured by the change in EQ-5D-5L, between baseline and 6 and 12 months post intervention. (41) The EQ-5D-5L is a patient-reported generic measure of HRQoL comprising five dimensions: mobility, self-care, usual activities, pain/discomfort and anxiety/depression. Responses to the 5 items (one for each dimension) result in a patient's health state that can be transformed into a utility score ranging between 0 (death) and 1 (full health), representing the quality of life of the health state. (41). The EQ-5D-5L is assessed at baseline and at 1, 3, 6 and 12 months post intervention.
- Change in characteristic attitudes and symptoms of depression from baseline to 3, 6 and 12 months post intervention. This will be measured by the change in Hospital Anxiety and Depression Scale (HADS) and in Pain Catastrophizing Scale (PCS) from baseline to 6 and 12 months. (42, 43) HADS is developed to detect anxiety and depression in patients with physical health problems. The questionnaire consists of 14 items: 7 items to measure anxiety and 7 items to measure depression. The PCS is often used in clinical settings to measure catastrophic thinking related to pain. The 13 item questionnaire consists of 3 subscales (magnification, rumination and helplessness) and asks patients to

Cocogen Trial

reflect on past painful experiences and to indicate the degree on which they experiences each of 13 thoughts of feelings on a 5- point scale (0 not at all and 4 all the time).

- Amount of Adverse Events and/or Serious Adverse Events. Active capture during each site visit to assess specific symptoms and adverse events that are relevant to chronic knee pain or RF treatment.

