- Costs in both intervention groups. Costs include health care related costs (e.g. intervention cost, medication), costs to patients and family (e.g. travel costs, out-of-pocket payments), and costs due to lost productivity. Complete individual level hospital resource use data (e.g. surgical intervention, diagnostic procedures, hospital admissions, outpatient clinic visits) will be measured using medical records and by means of a self-developed questionnaire to be completed by patients, based on the iMTA Medical Consumption Questionnaire as recommended in the Dutch guideline for economic evaluation. (44) The questionnaire will have a recall period of 3 months and will be administered repeatedly at baseline, 3, 6 and 12 months post intervention. The Dutch manual for costing research will be used to determine prices for each volume of resource use. (45)
- Cost-effectiveness will be expressed using incremental cost-effectiveness ratios (e.g. incremental cost per QALY, incremental cost per reduced point on the pain score, and incremental costs per additional treatment success). QALYs (Quality Adjusted Life Years) will be calculated by multiplying life years with the health-related quality of life during these life years as measured by the EQ-5D-5L.
- At 12 months in the osteoarthritis group, we ask if a total knee arthroplasty is performed and if so at which timepoint.
- All used questionnaires to retrieve the above mentioned outcome parameters can be found in Appendix D.

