7.2 Randomisation, blinding and treatment allocation

Final inclusion of a patient follows after written informed consent. Included patients will be subscribed by the central trial coordinator and the data management centre. The data management centre is responsible for the randomisation procedure, which will be performed with the software program CASTOR. Randomisation is justified because both treatments are similar with similar risks since the cooled radiofrequency is a modification of the conventional technique. The cooled radiofrequency however has the potential benefit of higher chance of therapy success (pain reduction) and longer duration of therapy success. Every patient from

Cocogen Trial

or the total knee arthroplasty group, or the osteoarthritis group, will be divided into one of the treatment groups at random so that half of every patient population (TKA and OA) received cooled and half conventional radiofrequency treatment. The randomisation ratio is 1:1. Patients in group 1 will receive conventional RF treatment, and patients in group 2 are being treated with cooled RF treatment.

The patients are treated by a pain physician who is not involved in the follow- up treatment. The blinding of each patient enrolled in this study is tested approximately 30 minutes after the treatment by asking the patient what they think they have received. At the 6 months follow- up, the patient is deblinded.

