9.2 Secondary study parameter(s)

All hypothesis testing will be explorative in nature, and thus secondary to describing the outcome measures. The confidence interval of the difference between groups will be used to test non-inferiority of conventional RF compared to cooled RF. In case the point estimate of the difference in proportion of treatment effect between groups will be below the non-inferiority limit, this will be suggestive of non-inferiority. In that case, we will use the results of this study to calculate the necessary sample size for a future randomized controlled non-inferiority trial.

Other secondary study parameters (MQS III, PGIC, duration of pain relief, OKS, the Timed Up and Go test, goniometry, HADS, PCS, EQ-5D-5L, performance of a TKA and the amount of Adverse Events and/or Serious Adverse Events) will be reported as mean or percentage difference including 95% confidence interval. Hypothesis testing will be performed using the independent t-test for continuous variables, and Fisher's Exact test for categorical variables. This will only be regarded as explorative in nature.

Cocogen Trial

COST EFFECTIVENESS ANALYSIS (CEA)

Economic evaluation comparing conventional to cooled RF treatment will be performed with a time horizon of 6 months. Cost-effectiveness will be assessed by evaluating the incremental cost-effectiveness ratios using several perspectives: societal cost per QALY (based on EQ-5D-5L), healthcare cost per reduced point on the pain score, and healthcare costs per additional treatment success. Standard bootstrap and sensitivity analysis will be performed to address uncertainty surrounding the findings.

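### As written, the cost-effectiveness analysis does not adjust QALYs or costs for baseline; with about 24 patients per arm this loses precision and leaves the incremental QALY open to chance imbalance

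*Protocol*

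**What the plan says.** Protocol section 7.1.2 defines the economic effect measure from utility levels: "QALYs (Quality Adjusted Life Years) will be calculated by multiplying life years with the health-related quality of life during these life years", with quality of life taken from the EQ-5D-5L. On timing, the same section says: "The EQ-5D-5L is assessed at baseline and at 1, 3, 6 and 12 months post intervention". The cost questionnaire has a 3-month recall and "will be administered repeatedly at baseline, 3, 6 and 12 months post intervention". Baseline values of both quantities will therefore be in the database, and the schedule in Appendix E confirms this.

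The CEA paragraph of section 9.2 sets a 6-month horizon and three ratios: societal cost per QALY, healthcare cost per point of pain reduction, and healthcare cost per additional treatment success. On uncertainty it says: "Standard bootstrap and sensitivity analysis will be performed to address uncertainty surrounding the findings". No covariate is named for incremental QALYs or incremental costs.

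On size, section 4.4 explains that "this means 12 patients in the conventional RF group and 12 in the cooled RF group", separately for osteoarthritis and post-arthroplasty patients, and concludes: "Hence, we will include a total of 48 patients". Section 7.2 adds: "The randomisation ratio is 1:1", with each of the two populations split in half between the treatments.

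**The concern.** Two of the three effect measures in the CEA, pain points and treatment success, are referenced to each patient's own baseline. The clinical EQ-5D-5L endpoint in 7.1.2 is also a change from baseline. The QALY is the exception: it is built from utility levels, so where a patient starts stays in the result. Costs are likewise totals.

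In a small trial the arms can start at somewhat different mean utilities by chance. Balancing on OA/TKA does not prevent this within each population. Because utility at later visits correlates with utility at baseline, an unadjusted comparison carries part of that starting difference into the incremental QALY. The protocol expects both arms to benefit similarly, so the true difference may be close to zero, and a small shift can then change the sign of the ratio's denominator.

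At stake is the study's secondary goal: an initial cost-effectiveness estimate that helps decide whether and how to build an economic evaluation into the later RCT.

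**Working it through.** **The plan's own figure.** 12 per arm × 2 arms × 2 populations = 48, which reproduces the stated total. Pooled over populations this is 48 / 2 = 24 per arm. The total rests on a rule of thumb, with no power calculation behind it.

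**Inputs.** From the protocol: n = 24 per arm; EQ-5D-5L at 0, 1, 3 and 6 months within the 6-month horizon. Assumed, because the protocol gives none of them: trapezoidal interpolation between visits, utility SD of 0.20 or 0.25, and equal correlation r between visits of 0.3, 0.5 or 0.7.

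**Step 1, weights in years.**
- Baseline: (1/2)/12 = 0.0417
- Month 1: ((1 + 2)/2)/12 = 0.125
- Month 3: ((2 + 3)/2)/12 = 0.2083
- Month 6: (3/2)/12 = 0.125

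They sum to 0.5. Baseline itself is 0.0417/0.5 = 8.3% of the total.

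**Step 2, chance baseline difference.** SE = SD × √(2/24). For SD 0.25 this is 0.0722; for SD 0.20 it is 0.0577.

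**Step 3, shift in incremental QALY per unit of baseline difference.** Slope = 0.0417 + r × (0.5 − 0.0417). This gives 0.179, 0.271 and 0.363 for r = 0.3, 0.5 and 0.7. At SD 0.25 and r = 0.5, a 1-SE imbalance shifts the result by 0.271 × 0.0722 = 0.0195. Only 0.0417 × 0.0722 = 0.003 of that comes from the baseline visit itself; the rest comes through correlation with later visits.

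**Step 4, precision.** Raw SE = SD × √[(1 − r)Σw² + r × 0.25] × √(2/24), with Σw² = 0.0764. At SD 0.25 and r = 0.5: 0.25 × √0.1632 × 0.2887 = 0.0292. The correlation of QALY with baseline is 0.271/√0.1632 = 0.67, so adjustment removes 0.67² ≈ 45% of the variance, and the SE becomes 0.0292 × √0.55 = 0.0216.

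| SD | r | 1-SE shift | Raw SE | Adjusted SE | Variance cut |
|---|---|---|---|---|---|
| 0.25 | 0.3 | 0.0129 | 0.0259 | 0.0224 | 25% |
| 0.25 | 0.5 | 0.0195 | 0.0292 | 0.0216 | 45% |
| 0.25 | 0.7 | 0.0262 | 0.0321 | 0.0186 | 66% |
| 0.20 | 0.3 | 0.0103 | 0.0206 | 0.0182 | 23% |
| 0.20 | 0.5 | 0.0156 | 0.0234 | 0.0176 | 44% |
| 0.20 | 0.7 | 0.0209 | 0.0257 | 0.0151 | 66% |

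The SD 0.25 rows come from the formulas. In the SD 0.20 rows, the SEs and variance cuts come from 20,000 simulated trials with no true difference, with the adjustment slope estimated in each trial.

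**Step 5, average and conditional error (same simulation).** Over all trials, the mean error of both estimators was below 0.0002 in absolute value. Among trials whose baseline difference exceeded 1 SE in one direction, the raw estimate was off by 0.016, 0.024 and 0.032 QALY for r = 0.3, 0.5 and 0.7. The adjusted estimate was off by at most 0.0002.

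**Costs.** The protocol gives no cost mean, SD or correlation, so no corresponding figure can be computed.

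**The case against.** A reader might infer more than the protocol supports, in four ways.

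- *That the cost-effectiveness result is biased.* It is not. Allocation is random and 1:1, and the simulated mean error is essentially zero without adjustment. What remains is lost precision and, equivalently, error conditional on the imbalance that happens to occur.
- *That the baseline difference enters the QALY directly.* Only 8.3% of the 6-month area is the baseline visit; most of the effect depends on the assumed correlation.
- *That the bootstrap repeats the imbalance in every resample.* The baseline difference varies across resamples around its observed value. The unadjusted interval therefore already covers this variation and is merely wider than necessary.
- *That the protocol chooses an unadjusted comparison.* It never says so. Section 7.1.2 defines a patient's QALY, and regression on baseline is compatible with that definition. The trapezoid is an assumption too.

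The strongest reply goes further: covariates in an economic model normally belong in an analysis plan, and none is at hand here. That has weight, and a plan naming the adjustment would settle the point. However, the protocol itself fixes the QALY formula, the horizon, the ratios and the uncertainty method. An analyst following that text literally would make an unadjusted comparison.

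It is also fair that the stakes are small. Even after adjustment, at SD 0.25 and r = 0.5, the 95% half-width is 1.96 × 0.0216 = 0.042 QALY, against 1.96 × 0.0292 = 0.057 before. The sign of a small true difference may stay unresolved either way. The QALY argument does not touch the two ratios based on pain and treatment success.

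**Conclusion.** The point holds as one about efficiency and robustness to chance imbalance. The economic method, taken as written, leaves unused baseline data that the trial collects. Across the assumed values, a 1-SE baseline utility imbalance shifts the incremental QALY by about 0.010 to 0.026, roughly half to four-fifths of its own raw SE, and adjustment cuts the variance by about 23% to 66%. If the CEA were run separately in each population, with 12 per arm, the 1-SE shift would be √2 times larger, about 0.015 to 0.037.

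These figures rest on assumed SDs, an equal-correlation pattern and trapezoidal interpolation. The direction of the result does not depend on the exact values, provided utilities correlate positively over time. The benefit on the cost side is plausible but unquantified. Importance is modest: this is an initial estimate from a pilot sized by rule of thumb, but it serves the stated secondary goal and the improvement needs no new data.

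**What to change.** Add to the CEA paragraph of Protocol section 9.2:

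- Incremental QALYs are estimated by regressing the 6-month QALY on treatment arm, baseline EQ-5D-5L utility and OA/TKA group.
- Incremental costs are estimated by regressing 6-month cost on treatment arm, baseline cost (3-month recall) and OA/TKA group.
- Both models are refitted in each bootstrap resample, with patients resampled within arm and OA/TKA group.

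If a separate analysis plan already says this, a cross-reference is enough. The unadjusted result can be kept as one of the sensitivity analyses already promised.

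The cost is one or two sentences and a few lines of code, with no new data, visits or patients. Each model spends two degrees of freedom beyond the arm term (three counting it): with 48 patients, residual degrees of freedom fall from 48 − 2 = 46 to 48 − 4 = 44.

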7.1.3 Other study parameters

Inclusion rates will also be monitored.

7.2 Randomisation, blinding and treatment allocation

Final inclusion of a patient follows after written informed consent. Included patients will be subscribed by the central trial coordinator and the data management centre. The data management centre is responsible for the randomisation procedure, which will be performed with the software program CASTOR. Randomisation is justified because both treatments are similar with similar risks since the cooled radiofrequency is a modification of the conventional technique. The cooled radiofrequency however has the potential benefit of higher chance of therapy success (pain reduction) and longer duration of therapy success. Every patient from

Cocogen Trial

or the total knee arthroplasty group, or the osteoarthritis group, will be divided into one of the treatment groups at random so that half of every patient population (TKA and OA) received cooled and half conventional radiofrequency treatment. The randomisation ratio is 1:1. Patients in group 1 will receive conventional RF treatment, and patients in group 2 are being treated with cooled RF treatment.

The patients are treated by a pain physician who is not involved in the follow- up treatment. The blinding of each patient enrolled in this study is tested approximately 30 minutes after the treatment by asking the patient what they think they have received. At the 6 months follow- up, the patient is deblinded.

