Nature and extent of the burden and risks associated with participation, benefit and group relatedness: After study enrolment and baseline intake, patients are treated and followed at 1, 3, 6 and 12 months after the initial intervention (total of 4 site visits, 1 online visit). Primary endpoint is 3 months post intervention. During the intake a physical examination is done. The treatment itself is performed without sedation and is generally well tolerated without side effects of complications. This study compares two active treatment therapies. Therefore, it is expected that patients from both treatment groups experience similar positive effects regarding pain relief and improved knee function.

Cocogen Trial

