3. STUDY DESIGN

This study is designed as a prospective, multicentre, double blind, randomised controlled non-inferiority pilot trial. The total follow up time is 12 months with follow up assessments at 1, 3, 6 and 12 months post intervention. It is estimated that the total duration of data collection will cover 2 year. Patients will be randomly selected for treatment with conventional RF treatment or cooled RF treatment of the SL, SM and IL genicular nerves. In total, three hospitals participate in this study: Ziekenhuis Oost-Limburg (Belgium), Maastricht UMC+ (Netherlands) and Rijnstate (Netherlands).

An overview of the main procedures that participants undergo is provided in figure 1, Appendix A.

Cocogen Trial

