7.3 Study procedures

Patients will be in follow up for 6 months. There are 4 site visits. T0 to collect baseline parameters after which the intervention is performed. T1 at one month post intervention. T2 at 3 months post intervention at which the primary endpoint is collected. T3 at 6 months post intervention.

Table 1 (Appendix E) provides an overview of all study procedures per follow up moment. There is a distinction between study procedures at site and study procedures at home.

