Appendix E

Table 1: Overview study procedures per site visit

Site visit	Study procedures at site	Study procedures at home
T0: baseline	- MQS III	- NRS
	- Goniometry	- Is pain acceptable?
	- Timed up and go test	- Medication list
		- OKS
		- EQ-5D-5L
		- HADS
		- PCS
		- Cost diary
T1: 1 months	- Adverse Events	- NRS
post	- MQS III	- Is pain acceptable?
intervention		- PGIC
		- Medication list
		- EQ5-5D-5L
		- Cost diary
T2: 3 months	- Adverse Events	- NRS
post	- MQS III	- Is pain acceptable?
intervention	- Goniometry	- PGIC
	- Timed up and go test	- Medication list
		- OKS
		- EQ-5D-5L
		- Cost diary
		- HADS
		- PCS
T3: 6 months	- Adverse Events	- NRS
post	- MQS III	- Is pain acceptable?
intervention	- Goniometry	- PGIC
	- Timed up and go test	- Medication list
		- Cost diary
		- OKS
		- EQ-5D-5L
		- HADS
		- PCS
T4: 12 months	/	- NRS

Cocogen Trial

- Is pain acceptable?
- PGIC
- Medication list
- Cost diary
- OKS
- EQ-5D-5L
- HADS
- PCS
- Adverse Events
- Performance of TKA?

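### Patients learn their allocation at 6 months, so the 12-month secondary outcomes of a trial described as double blind are unblinded

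*Protocol*

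**What the plan says.** On blinding and length of follow-up, the protocol says:

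- Section 3: "This study is designed as a prospective, multicentre, double blind, randomised controlled non-inferiority pilot trial", and "The total follow up time is 12 months with follow up assessments at 1, 3, 6 and 12 months post intervention".
- Section 7.2: at the 6-month follow-up, "the patient is deblinded". The same section credits cooled RF with a possible advantage in both the chance and the duration of success.
- Section 7.3: "Patients will be in follow up for 6 months", with site visits T0 to T3 only.
- Summary, paragraph on burden and risks: "total of 4 site visits, 1 online visit", which makes the 12-month contact (T4) the online one.

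On what is measured at 12 months:

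- Appendix E, Table 1, has no site procedure at T4 and puts every item in the home column.
- Section 7.1.2 states that the objective function measures are not taken at 12 months, and that knee replacement in the osteoarthritis group is ascertained by asking.

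Sections 4.2, 5.2 and 5.3 allow any other treatment or medication during follow-up, provided it is documented.

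**The concern.** A blinding claim covers the outcomes collected while the blind is in force. Here the patient is told the allocation about six months before the last assessment, and that assessment consists almost entirely of what the patient reports. The protocol neither limits the double-blind description to the first 6 months nor labels the 12-month results as unblinded.

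Two routes to bias open up:

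- **Expectation.** A patient who knows which technique was used may rate pain, function or global change differently.
- **Behaviour.** Because co-treatment is unrestricted, a patient who knows the allocation may be more or less inclined to seek it. Additional therapy is part of the definition that ends the period of pain relief in section 7.1.2.

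The likely direction is not neutral. The protocol's own text expects a longer effect from cooled RF, and durability is what the period after month 6 is there to show. The pilot is also meant to give effect-size estimates for secondary as well as primary outcomes (section 4.4) and to mirror the future trial closely (section 1), so the same disclosure point could be carried forward.

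**Working it through.** The protocol gives no figure to reproduce here. The check sets the disclosure time against the schedule and counts items.

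**1. Timing.** Follow-up assessments are at 1, 3, 6 and 12 months. Disclosure is at 6 months, so 12 − 6 = 6 months of follow-up come after it. One of the four follow-up time points (T4) falls wholly in that period.

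**2. Content of T4 (Table 1).**
- On site: 0 items.
- At home: NRS, acceptability of pain, PGIC, medication list, cost diary, OKS, EQ-5D-5L, HADS and PCS (9 items), plus adverse events and "Performance of TKA" (2 items). Total 9 + 2 = 11.
- The nine are patient ratings, questionnaires or diaries. The other two are also obtained remotely.
- Goniometry and Timed Up and Go, on the schedule at T0, T2 and T3, are absent.
- One qualification: section 7.1.2 takes hospital resource use partly from medical records, so the 12-month information is nearly all, not all, patient-reported.

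**3. Duration of pain relief (section 7.1.2).** The interval lasts while NRS reduction exceeds 50% or pain remains acceptable, without additional therapy. A patient whose relief ended before month 6 has a duration fixed under blinding. For a patient still in relief at month 6, the rest of the interval depends on ratings and treatment choices made with the allocation known.

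**4. Knee replacement.** This is an event, not a rating. The report of it is hard to bias, but the decision to operate after month 6 could be influenced.

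**5. The 6-month data.** At T3, Table 1 lists 4 items on site (adverse events, MQS III, goniometry, Timed Up and Go) and 9 at home, including NRS, EQ-5D-5L and the cost diary. Section 7.2 discloses at the 6-month follow-up without saying whether the home items must be in first. The window of four days either side of a time point in section 7.1.1 does not settle the order. The economic evaluation in section 9.2 has a 6-month horizon and draws on these items.

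**6. What lies outside the problem.** The primary endpoint is at 3 months (section 7.1.1), before disclosure. The 12-month costs and EQ-5D-5L fall beyond the economic horizon.

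**7. Length of follow-up.** Section 7.3 gives 6 months; section 3, section 7.1.2 and Table 1 give 12. The four site visits in section 7.3 agree with the Summary; the stated length does not.

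**The case against.** The strongest reply is that disclosure at 6 months is stated openly and nothing important rests on what follows. The primary endpoint precedes it, the economic horizon stops at 6 months, sections 9.1 and 9.2 call the non-inferiority comparison and all testing exploratory, and the main purpose is to inform a later trial. No stated decision depends on the 12-month data. That reply stands as to weight. It does not answer the point that the 12-month outcomes are declared secondary parameters, presented under a double-blind label that does not apply to them, and that analysis cannot restore the blind once a patient has been told.

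A reader might go further than the text allows in four ways:

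- **That the main result is at risk.** It is not; it is collected three months before disclosure.
- **That the 6-month data are already compromised.** The protocol is silent on the order of questionnaires and disclosure. Silence is a reason to fix the order, not evidence that it goes wrong.
- **That all of duration of pain relief is biased.** Only patients still in relief at month 6 are exposed.
- **That the 12-month contact was added late and the disclosure point forgotten.** The 6 months in section 7.3 might prompt that thought, but nothing in the document shows how the text arose. The inconsistency is a separate matter.

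**Conclusion.** The point holds in limited form. All 11 items at T4, one of four follow-up time points, are collected after patients know their allocation, nearly all by patient report and with no objective function test. The 12-month secondary outcomes, and duration of pain relief for those still in relief at month 6, should be regarded as unblinded. Co-treatment and the decision for knee replacement after month 6 could also be influenced. The 6-month outcomes and the economic evaluation are safe only on the assumption that the T3 home questionnaires are completed before disclosure.

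The size of any bias cannot be worked out from the protocol: it gives neither a standard deviation for the NRS nor any basis for an expectation effect, so a figure in NRS points or standard errors would only restate its assumptions. The count above is the defensible measure.

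This is a recommended change, not a condition for the trial to answer its primary question.

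**What to change.** **Preferred.** Amend section 7.2 so that allocation is disclosed to a patient only after that patient's T4 data have been received. Record the date and reason of any earlier disclosure.

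**If disclosure at 6 months is kept.** Require the T3 data, including the home questionnaires, to be recorded first. Limit the double-blind description to the first 6 months, and report the 12-month outcomes, and the part of duration of pain relief after disclosure, as unblinded.

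**In either case.** Reconcile the 6 months of follow-up in section 7.3 with the 12 months in section 3, section 7.1.2 and Table 1.

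**Cost.** The preferred change needs a short amendment and matching patient information, with no extra visits or patients. Its downside is that patients wait up to 6 months longer to learn which treatment they had. The alternative avoids that wait but leaves the 12-month comparison unblinded.
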